7.3.2 AE/SAE Documentation

All negative changes in health reported by participants will be recorded on standardized AE or SAE forms, as appropriate. Each adverse event will be assigned an AE number and will be recorded on a separate AE form to avoid duplication in reporting. For each AE, clinical coordinators will record the date of onset and resolution of the AE and record the nature or type of AE. In consultation with the principal investigator, coordinators will also indicate whether any indicate whether any specific action such as discontinuation of the study intervention was taken in response to the AE.

Using the Common Terminology Criteria for Adverse Events (CTCAE) system, all adverse events will be graded in severity using the 5-point CTCAE scale. According to this scale, AEs are considered grade 1 if they represent only mild symptoms or asymptomatic laboratory findings; grade 2 if they cause moderate symptoms that limit instrumental activities of daily living (shopping, transportation, household tasks); grade 3 if they are serious or disabling events or result in hospitalization or prolongation of hospitalization without being directly life-threatening; grade 4 if they are life-threatening events in which the participant is at risk of death at the time of the event if immediate intervention is not undertaken; or grade 5 if they are fatal adverse events.

Each serious adverse event will be assigned an SAE number and recorded on an SAE form. Similar to regular AEs, clinical coordinators will record the date of onset and resolution of each SAE and record the nature or type of SAE. Coordinators will also document any treatment provided for the SAE, indicate any laboratory or other clinical data obtained about the SAE, indicate the participant's condition at the time of reporting of the SAE, and indicate whether any specific action such as study discontinuation was taken in response to the SAE. Each SAE form will be reviewed and signed by the principal investigator, who will use a standard attribution scale to indicate the potential relationship between any SAEs and study interventions (not, unlikely, possible, probably, or definitely related to study intervention).

7.4 Reporting Procedures

7.4.1 SAE Reporting

- Clinical coordinators will notify the principal investigator immediately when a SAE is discovered, in addition to filling out a standardized SAE form that will be reviewed and signed by the principal investigator (see section above regarding SAE documentation).
- The principal investigator will then report any deaths to the institutional review board at the University of California San Francisco, the independent Data and Safety Monitor (DSM), and the NIDDK program officer within 24 hours of awareness of the event.
- Other unexpected serious adverse events that are potentially intervention-related will be reported by the principal investigator to the UCSF IRB, the DSM, and the NIDDK Program Officer within 48 hours of learning of the event.
- Anticipated or unrelated SAEs will be handled in a less urgent manner but will also be reported to the UCSF IRB and the DSM within 1 week of awareness of the event, and at least quarterly to the NIDDK Program Officer. Of note, no SAEs that are directly related to the study procedures are currently anticipated.

7.4.2 Non-Serious AE Reporting

- If a clinical coordinator discovers an AE that does not meet the definition of a SAE but may still pose a substantial risk of harm to a participant and is potentially associated with study interventions or procedures, he/she

- will report the AE to the principal investigator within 1 working day, in addition to filling out a standardized AE form.
- Cumulative trends in all non-serious adverse events will be reviewed by the principal investigator and the DSM at scheduled DSM meetings (see below for DSM meeting schedule). More frequent cumulative review of non-serious adverse events may be performed if recommended by the DSM or desired by the principal investigator.
- Although the UCSF IRB does not require reporting of non-serious AEs to the UCSF IRB, the principal investigator may consult the UCSF IRB for input on handling of non-serious AEs if they may still pose a substantial risk of harm to a participant or are potentially associated with study interventions or procedures.

7.5 Follow-up for AEs/SAEs

From the time that they are first reported by participants until the end of the study, AEs and SAEs will be followed until resolved or considered stable. At each scheduled follow-up contact after initial discovery of an AE or SAE, a clinical coordinator will assess whether the AE or SAE is continuing or has resolved, and will update information about event status on the AE or SAE form, as appropriate. For SAEs, the clinical coordinator or principal investigator will also make more active attempts to communicate with participants in between scheduled study visits (with their permission) in order to monitor resolution of SAEs.

7.6 Independent Safety Monitoring

The conduct of the study and safety of participants will be evaluated by an independent Data and Safety Monitor (DSM), who will be a clinical researcher experienced with designing, implementing, and monitoring safety in therapeutic interventions studies as well as a practicing clinician. The DSM is independent of the investigators and staff participating in the study, and has no financial ties to the outcome of the study. The DSM will periodically review the conduct and outcomes of the study and provide feedback to the investigators, with particular attention to protecting the safety of the participants.

Prior to initiation of the trial, the DSM will review and approve the study design and plans for recruitment, adherence, interventions, data quality, and safety monitoring. Approximately twice a year after recruitment begins, the DSM will evaluate the adequacy and timeliness of participant recruitment, adherence to the protocol, and the potential of the study to meet the stated goals; evaluate the quality and integrity of the data, including adequacy of data management and data security procedures; evaluate participant safety including trends in adverse events and relationship to the study procedures; consider factors external to the study when relevant information, such as scientific developments, may have an impact on the safety of the participants or the ethical conduct of the study; and make recommendations, if necessary, to the investigators and the NIDDK on continuation, termination, or other modifications of the study protocol.

The DSM will periodically review aggregate trial data according to the Data and Safety Monitoring Plan (DSMP). An emergency meeting may also be called by the principal investigator at any time should questions of participant safety arise. Each review will include an assessment of the adequacy and timeliness of participant recruitment, adherence to the visit and intervention protocols, data quality and

timeliness, adverse effects, and participant safety. Interim reports for the DSM will be prepared by a biostatistician contracted by the Women's Health Clinical Research Center, and sent to the DSM at least 5 days prior to a pre-scheduled meeting or conference call.

After each interim review, the DSM will provide a signed statement that indicates whether the study should continue, terminate, or be altered based on ability to meet study recruitment and data quality goals and participant safety. He will include any recommendations for changes to the protocol if necessary to enhance participant safety or potentiate the ability of the trial to answer the research hypotheses. This statement will be provided to the principal investigator and will be sent to the UCSF IRB and to the NIDDK program officer. All materials, discussions, and proceedings of the DSM process will be completely confidential.

8. INTERVENTION DISCONTINUATION

Participation in the yoga and/or control interventions may be discontinued if determined to be necessary to protect the safety of a participant. The decision to discontinue participation in therapeutic interventions will be made on a case-by-case by the principal investigator, with input from the DSM if needed. Possible reasons for discontinuation of the therapeutic intervention may include: 1) development of a clinically significant adverse event limiting a participant's ability to safely take part in yoga or stretching/strengthening practice; 2) disruptive behavior exhibited by a participant during intervention classes or study visits that endangers the safety or comfort of other study participants, class instructors, or study staff; or 3) decision to terminate the study by the IRB, NIDDK, or other regulatory bodies.

Participants may also decide that they want to discontinue participation in interventions, even if study staff urge them to complete assigned 12-week intervention programs.

In the event that participation in yoga or control intervention programs is discontinued, but the principal investigator and the participant feel it is safe, feasible, and appropriate for the participant to continue to provide outcomes data, the participant will continue to be followed through 36 weeks (until the original expected 24-week post-intervention assessment) to collect outcomes data. If follow-up assessments are continued, no modifications to the schedule of follow-up assessments will be made unless necessary to protect the safety of participants or to accommodate limitations in function resulting from an adverse event.

Follow-up assessments in participants who have discontinued the therapeutic interventions will not include continued evaluation of adherence to group classes or home practice, assessment of yoga posture or practice adherence self-efficacy, or independent evaluation of participants' success in performing yoga postures or stretching/strengthening exercises.

9. STATISTICAL CONSIDERATIONS

9.1 General Design Issues

A randomized, parallel-group, superiority trial design has been selected as the being the most appropriate design for the scientific goals of this research. Eligible participants will be randomly assigned in equal ratios to the yoga versus control interventions, with equivalent time and attention spent on study intervention and assessment procedures in both groups.

A non-specific muscle stretching-strengthening exercise program has been selected as an active behavioral control intervention for this trial. Although this control

intervention may offer non-specific benefits for participants' health, the investigators believe that it is unlikely to improve incontinence symptoms to the same extent as the yoga intervention. Inclusion of this plausible control intervention will also minimize differential expectations of treatment benefit between participants in the two groups, thus promoting similar adherence to interventions and visits in both groups.

9.2 Sample Size

Sample size has been calculated based on parameter estimates derived from both the investigators' past pilot studies on yoga as well as other group-based incontinence intervention trials conducted by study team members.¹⁰³ Assumptions include: a) average baseline frequency of incontinence of ~23-24 episodes/week; b) standard deviation (SD) of change in incontinence frequency of ~14.4; c) correlation between outcome values of ~0.59; and d) loss of ~15% by 3 months. Assuming a ~50% decrease in incontinence frequency among controls (which is the threshold at which women with daily incontinence start to perceive meaningful benefit from treatment¹⁸), the team will power the study to detect a between-group difference in reduction in incontinence of at least 20% in the yoga versus stretching/strengthening control group (corresponding to a \geq 70% reduction in frequency of incontinence in the yoga group) at 3 months. Under these assumptions, a sample size of 240 (120 per group) will provide 80% power in 2-sided tests with 5% type-I error to detect a between-group difference in reduction in the primary outcome of total incontinence frequency of at least 20% in the yoga vs. control arm. With regard to secondary outcomes, this sample will also provide 80% power to detect moderate between-group differences of 0.26 to 0.39 SDs, assuming intraclass correlation of outcomes in the range of 0.4-0.8.

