9.6 Data Analyses

9.6.1 Analyses to address main objectives

Objective 1: To determine the efficacy of a group-based yoga intervention in reducing the frequency of urinary incontinence in ambulatory midlife and older women.

Hypothesis 1A: Ambulatory incontinent women randomized to the yoga intervention will demonstrate at least a 20% greater decrease in total incontinence frequency (measured by validated voiding diaries) over 12 weeks, compared to women randomized to the control intervention.

Hypothesis 1B: If improvements in total incontinence frequency are observed at 12 weeks, these improvements will be sustained 12 and 24 weeks after the end of the intervention programs.

Planned analyses: Intervention effects on the primary outcome of total incontinence frequency will be estimated using a linear mixed model (LMM) for changes since baseline in the overall frequency of any incontinence episodes at 6 and 12 weeks, adjusting for baseline incontinence frequency. Analyses will be by intention to treat, according to intervention group assignment, and without regard to adherence to intervention classes or practice. The LMM will account for clustering using nested random effects for group intervention class series and individual participant. In addition to fixed effects for study location and type of incontinence, the LMM will include terms for intervention, time, and the time-by-intervention interaction, thus allowing for secular trends in controls, as well as different intervention effects at 6 and 12 weeks. The intervention effect will be summarized by an orthogonal contrast capturing any linear trend across 6 and 12 weeks; this makes use of information for participants with 6 but not 12 week outcomes. If the yoga intervention appears effective over 12 weeks, we will also assess maintenance of effects over time, by comparing changes since baseline at 12 weeks with those at 24 and 36 weeks, using an additional LMM. Intervention effects will again be summarized by an orthogonal contrast for linear trend across the three time points.

Objective 2: To determine the efficacy of a group-based yoga intervention in reducing the frequency of type- and context-specific urinary incontinence in ambulatory middle-aged and older women.

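### Section 9.2 labels 14.4 as an SD of change, but its 80% power appears to use 14.4 as a single-visit SD; either the label or the power needs correcting, and the printed inputs do not settle which

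*Combined protocol and SAP*

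**What the plan says.** Section 9.2 (Sample Size) lists the assumptions: "average baseline frequency of incontinence of ~23-24 episodes/week", then "standard deviation (SD) of change in incontinence frequency of ~14.4; c) correlation between outcome values of ~0.59; and d) loss of ~15% by 3 months". It assumes a fall of about 50% in controls and targets "a between-group difference in reduction in incontinence of at least 20% in the yoga versus stretching/strengthening control group", that is, about 70% against 50%. It concludes that "a sample size of 240 (120 per group) will provide 80% power in 2-sided tests with 5% type-I error". The section gives no formula and no SD at baseline or at 12 weeks, and it does not say which two values the 0.59 correlates.

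Section 9.6.1 (Objective 1, planned analyses) models "changes since baseline in the overall frequency of any incontinence episodes at 6 and 12 weeks, adjusting for baseline incontinence frequency". The primary comparison is therefore baseline-adjusted.

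Section 9.2 also gives a detectable range for secondary outcomes: 0.26 to 0.39 SD for correlations between 0.4 and 0.8.

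**The concern.** In a baseline-adjusted comparison, the SD of the follow-up value is reduced by sqrt(1-r^2), where r is the correlation between baseline and follow-up. An SD of change is a different quantity. With a common SD sigma at both visits it equals sigma*sqrt(2(1-r)), so the correlation is already in it. Multiplying an SD of change by sqrt(1-r^2), with that same r, uses the correlation twice and makes the residual SD too small when the two visit SDs are equal.

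The 80% is the trial's stated power for its primary question, and Version 9.0 set N at 240 on this basis. If the labels in 9.2 are right and the visit SDs are equal, the chance of missing a true 70% versus 50% difference is about 26% rather than 20%, and a null result would be read with more confidence than the design supports.

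**Working it through.** **Inputs (section 9.2).** 120 per arm, 15% loss, so 120 x 0.85 = 102 per arm. Two-sided 5%. Baseline 23, 23.5 or 24 episodes per week, so the difference is 0.20 x baseline = 4.6, 4.7 or 4.8. SD 14.4, r = 0.59. Power is from the two-sample noncentral t; the normal approximation is about 0.4 points higher.

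**Step 1: reproduce the printed 80%.**
- 14.4 as printed, with no baseline adjustment: 62.2 / 64.1 / 65.9%.
- 14.4 x sqrt(1 - 0.59^2) = 14.4 x 0.807 = 11.63: 80.3 / 81.9 / 83.5%.

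The second line returns the stated figure at the lower end of the baseline range.

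**Step 2: do other figures in the plan point to the same factor?**
- Secondary range: 2.80 x sqrt(2/n) x sqrt(1-r^2) with n = 85 per arm gives 0.394 at r = 0.4 and 0.258 at r = 0.8, matching the printed 0.39 and 0.26. The factor sqrt((1+r)/2), which would convert an SD of change, gives 0.36 and 0.41, which rises with r and cannot match.
- Sample sizes: with residual SD 11.63 and 15% loss, 80% power needs about 247 women at 22.5 per week and 236 at 23. The change summary sets 250 for 22-23 per week (Version 8.0) and 240 for 23-24 (Version 9.0).
- At 25 per week, the baseline that Version 8.0 replaced, the same formula gives about 200 women. After 15% loss that is 85 per arm, the number that fits the secondary range. That 200 was ever the planned N is an inference; the visible text does not give it.

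So sqrt(1-r^2) applied to 14.4 is very probably the calculation behind section 9.2.

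**Step 3: use the inputs as labelled, with equal SDs at both visits (assumption).**
- sigma = 14.4 / sqrt(2 x 0.41) = 15.90.
- Residual SD = 15.90 x 0.807 = 12.84, equivalently 14.4 x sqrt((1 + 0.59)/2).
- Power with 102 per arm: 72.1 / 73.9 / 75.7%.
- Difference detectable with 80% power: 2.80 x 12.84 x sqrt(2/102) = 5.04 per week, and 5.04 / 23.5 = 21% of baseline.
- With all 120 per arm analysed and loss ignored: 78.9 / 80.6 / 82.2%.

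**Step 4: relax the equal-SD assumption.** Let k be the 12-week SD divided by the baseline SD. Then

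residual SD = k x 14.4 x sqrt((1 - r^2) / (1 + k^2 - 2rk)).

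At 23.5 per week with 102 per arm:

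| k | Residual SD | Power |
|---|---|---|
| 1.1 | 13.39 | 70% |
| 1.0 | 12.84 | 74% |
| 0.9 | 12.10 | 79% |
| 0.88 | 11.93 | 80% |
| 0.8 | 11.15 | 85% |

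The residual SD equals 11.63 exactly at k = 1/(2r) = 0.847. A modest fall in spread between baseline and 12 weeks therefore gives 80% with the correlation used once.

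**The case against.** Four points can be made for the plan.

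- **Equal SDs are not stated.** The plan assumes mean falls of 50% and 70% in a count that cannot go below zero, so a smaller SD at 12 weeks is plausible, and k = 0.88 already gives 80%. This stands. A reader might infer that 80% can be reached only by counting the correlation twice, or that the printed power cannot follow from the printed inputs. The documents support neither, because the inputs do not fix the power.
- **The fault may be only a label.** If 14.4 is the SD of the outcome at one visit, or 0.59 is the correlation of baseline with change, 11.63 is the right residual SD and 80% stands. The secondary range fits a mislabelled SD as well as a double count. This also stands; a wrong label cannot be told from a wrong calculation here.
- **74% is not the power of the planned model.** Section 9.6.1 uses 6- and 12-week data, including women with only the 6-week value. Illustrative calculations, assuming equal SDs, correlation 0.59 between all visits and 6-week data for women lost later, give about 77% if half the effect is present at 6 weeks and about 84% if three-quarters is. They ignore class clustering, and section 9.2 itself describes a comparison at 3 months. This limits the 74% to a single-visit comparison.
- **The gap is small and every input is approximate.** It is 6 points of power, or 21% rather than 20% detectable. True, but N was re-set by moving the assumed baseline by about one episode per week, so an input of this weight should be labelled correctly.

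The other route to about 80%, residual SD 12.84 with no loss, is a weaker defence because section 9.2 lists the 15% loss among its assumptions.

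**Conclusion.** The point holds in a limited form. Under the usual equal-SD convention, the inputs as labelled do not give the stated 80% with the stated loss. They give about 74% (72-76% over 23-24 episodes per week) for a single-visit, baseline-adjusted comparison, with about 5.0 episodes per week (21% of baseline) detectable at 80% power. This rests on three assumptions: 14.4 is truly an SD of change, 0.59 is the baseline to 12-week correlation, and the SDs at the two visits are equal. The documents confirm the first by label only, leave the second open, and are silent on the third. Between SD ratios of 1.1 and 0.8 the same inputs give 70% to 85%.

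It would be wrong to conclude that the trial has 74% power. What can be concluded is that section 9.2 very probably applied a single-visit factor to a figure it calls an SD of change, so either the label or the power needs correcting, or the missing SDs must be printed to support the 80%.

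**What to change.** Keep N = 240 and check 14.4 and 0.59 against the source data. Then, in section 9.2:

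1. If 14.4 is the SD of the outcome at one visit (at 12 weeks, or common to both visits), delete the words 'of change' and keep 80%.
2. If 0.59 is the correlation of baseline with change, relabel it so; the 80% again stands.
3. If 14.4 is the SD of change and 0.59 the baseline to 12-week correlation, print the baseline and 12-week SDs, compute the residual SD with the step 4 formula, and restate the power after 15% loss. That is about 74% only if the two SDs prove equal; 74% should not replace 80% unconditionally.

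In every case, state the formula and name the visits that 0.59 links. The cost is one look at the source data, one recalculation and a few words in section 9.2. No participants or procedures are added. The stated power may become somewhat less favourable.

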9.3 Randomization and Blinding

Randomization to the yoga or control intervention group will be performed by computer algorithm, with proof of eligibility required before assignment. Randomization will be implemented using randomly permuted blocks of sizes 2 and 4, and will also be stratified by clinical type of incontinence (i.e., stress-predominant, urgency-predominant), to ensure adequacy of randomization within types. To avoid manipulation, standard allocation concealment procedures will be followed.¹⁰² An analyst will prepare sealed, opaque envelopes containing group assignment, numbered consecutively with the randomization sequence numbers. At the baseline visit, when eligibility and incontinence type have been confirmed, coordinators will enter the date, participant name, and study ID in the randomization log and select the next numbered envelope to determine group assignment. All envelopes will be retained for review; randomization dates and times should follow the order of the sequence numbers, providing a check on validity.

Due to the behavioral nature of the intervention, participants cannot be blinded to intervention assignment, nor can study staff responsible for administering interventions or monitoring adherence to interventions. However, study investigators and staff members who are not involved in administering interventions or monitoring adherence to interventions will be blinded.

Diary data used to evaluate primary and secondary efficacy outcomes will be abstracted by blinded analysts. Study-wide unblinding for the 12-week intervention period will take place when data from all dataforms and study measurements for the 12-week intervention period have been entered into the database for all participants,

data cleaning for this period has been completed, and the principal investigator has declared the 12-week study dataset to be complete. Unblinding of study investigators or staff prior to the study-wide unblinding date will be undertaken only in exceptional circumstances in which knowledge of intervention assignment is essential to guide treatment or to protect the safety of a participant.

